- After a careful review of the safety, tolerability and PK data from all dose groups from the stage 3 CKD cohorts, the Data and Safety Monitoring Board (DSMB) will determine whether to proceed to the stage 4 CKD cohorts. If the determination by the DSMB allows to proceed to the stage 4 CKD cohorts, subjects with stage 4 CKD will be in 2 groups of 6 each, for a total of 12 subjects, evaluating escalating single dose of SnPP starting with a dose of 27 mg SnPP followed by 90 mg SnPP. Dose-escalation from one dose level to the next will only be allowed after a careful review of the safety, tolerability and PK data from the prior dose group as determined by the Data and Safety Monitoring Board (DSMB).
- Subjects will be followed for 28 days after the dose of SnPP. Response biomarkers will be assessed at baseline and 2, 4, 8, 12, 18, 24, 48, 72, 96 and 168 hours after study drug administration. Safety will be assessed for up to 28 days after study drug administration.
- Blood samples for SnPP pharmacokinetic analysis will be assessed at baseline and 1, 2, 3, 4, 6, 8, 12, 18, and 24 hours after study drug administration. These data will be used in the dose escalation decision making review process along with the safety and tolerability of the previous dose. Urine samples will be collected and centrifuged and analyzed for subject responsiveness to SnPP therapy.
- Urinary Clearance of SnPP will be assessed by the measurement of tin in a 24-hour urine sample.

- Total study duration will be 29 days for each subject, in addition to a screening period of up to 14 days. Up to a total of 42 subjects consisting of 18 healthy volunteers and 24 chronic kidney disease (stage 3-4) subjects will receive single escalating doses of SnPP.

For a complete list of assessments performed throughout the study, see Time and Events Schedule ([Section 10](#)).

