7 STATISTICAL METHODS OF ANALYSIS

7.1 General Principles

The statistical analyses will be reported using summary tables, listings, and figures (TLFs). All analyses and tabulations will be performed using SAS® Version 9.4 or later. Continuous variables will be summarized using descriptive statistics (sample size [n], mean, standard deviation [SD], minimum, median, and maximum). Categorical variables will be tabulated with number and percentage of subjects. Unless otherwise noted, percentages will be based on the number of subjects from the population, as appropriate.

Individual subject data will be provided in listings. All listings will be sorted by dose group (1 = 9mg SnPP, 2 = 27mg SnPP, 3 = 90mg SnPP), stratum (CKD Stage 3 patients and CKD Stage 4 patients versus healthy volunteer subjects), and collection date and time, where applicable,

Unless otherwise noted, tabulations of categorical data will present only those categories appearing in the data.

7.1.1 *Handling Missing Values*

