7.6 Efficacy Analysis

7.6.1 *Percent Change in Response Biomarkers*

The efficacy endpoint is the percent change (PCH_T) in each response biomarker relative to the Baseline period.

PCH_T will be calculated as $100 \times (T - B)/B$, where T and B are Response biomarker at 2, 4, 8, 12, 18, 24, 48, 72, 96 and 168 hours post dose (T) and baseline period (B).

PCH_T will be analyzed using a Mixed-Effect Model for Repeated Measure (MMRM) as follows:

- A 2-way MMRM pooling stage 3 and stage 4 CKD patients and healthy subjects together
- A 2-way MMRM pooling stage 3 and stage 4 CKD patients together
- A 2-way MMRM for Healthy subjects

The model will include dose level, visit (2, 4, 8, 12, 18, 24, 48, 72, 96 and 168 hours), and dose-by-visit interaction as factors and baseline response biomarker as covariate. The model parameters will be estimated using the restricted maximum likelihood method with the toeplitz variance-covariance matrix and Kenward-Roger estimate for the denominator degrees of freedom. The between dose comparison will be performed using contrast in the main effect and the simple contrast at each time point. Least squares mean (LSM) and the associated 95% confidence interval (CI) for each dose level will be presented. The difference in LSM between doses and the 95% CI for the difference will also be presented. Results will be presented for the pooled population, as well as for the CKD and healthy populations separately.

Additionally, LSM for each dose group will be plotted over time for the CKD patients and healthy volunteers pooled population as well as for each population separately. Dose response relationship will be examined graphically and may be analyzed where appropriate.

A sample SAS code is provided as follows. The code assumes that “visit” has 10 values (2, 4, 8, 12, 18, 24, 48, 72, 96 and 168 hours), “dose” is coded as 1 = 9 mg SnPP, 2 = 27 mg SnPP, and 3 = 90 mg SnPP, “ckd” is coded as 2= CKD patients and healthy volunteers pooled, 1 = patients with CKD, 0 = healthy volunteers, and “resp” = PCH_T, the % change from baseline being analyzed.

```
ODS OUTPUT LSMEANS=lsm DIFFS=diff ESTIMATE=estm;
PROC MIXED DATA=XXXX;
BY ckd;
CLASS dose usubjid visit;
MODEL resp = base visit dose dose*visit / DDF=KR;
REPEATED visit / SUBJECT=usubjid(dose) TYPE=UN;
ESTIMATE "90 mg v 27 mg overall" dose 1 0 -1;
LSMEANS dose / DIFF CL;
ESTIMATE "90 mg v 27 mg @ 168 hours " dose 0 -1 1
dose*visit 0 0 0 0 0 0 0 0 0 0
0 0 0 0 0 0 0 0 0 -1

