0 0 0 0 0 0 0 0 0 1 / CL;
RUN;
ODS OUTPUT CLOSE;
```

Note: Depending on the convergence status in the computation, Toeplitz (toep), 1st order autoregressive AR(1), and compound symmetry (CV) variance-covariance matrix will be applied sequentially. The final analysis will be based on the first matrix leading to the convergence in the computation.

7.6.2 *Absolute Change*

In addition to the percent changes from baseline, absolute change from baseline will also be analyzed using MMRM. The method of analysis will be identical after replacing variable “resp” with “T-B” in [Section 7.6.1](#).

7.6.3 *Responder Analysis*

Repeated measures responder analyses will be fitted using the generalized estimating equations (GEE) with PROC GENMOD in SAS for the proportion of patients reporting a response (defined as a 50% or greater reduction in each response biomarker from baseline) at each Visit.

The model set up is similar to MMRM ([Section 7.6.1](#)). A logit link function will be used for this binary response variable. The unstructured within-subject variance-covariance matrix will be assumed. If computational convergence is an issue, other types of variance-covariance matrices will be explored. Odds ratios and 95% confidence intervals will be presented comparing proportion of responders between dose levels at each assessment timepoint. Results will be presented for the pooled population, as well as for the CKD and healthy populations separately.

Sample SAS code is given below. Variable “resp” is coded as 1 = Responder and 0 = Non-Responder.

```
ODS OUTPUT LSMEANS=lsm DIFFS=diff ESTIMATE=estm;
PROC GENMOD DATA=dataset;
  BY ckd;
  CLASS visit dose usubjid;
  MODEL resp(EVENT='1') = base visit dose dose*visit / LINK=LOGIT DIST=BIN;
  REPEATED SUBJECT = usubjid /TYPE=UN;
  LSMEANS dose / DIFF CL;
RUN;
ODS OUTPUT CLOSE;
```

7.6.4 *Exploratory analysis*

Percent change and change in each response biomarker will be analyzed using the Cochran-Mantel-Haensel (CMH) test stratified by baseline. In the stratification, baseline will be divided into quintiles based on the pooled CKD and Healthy subjects in the MITT population. Between group comparison will be carried out at each time point using the CMH test for row mean score difference (RMS) with the modified ridit scores. Analysis will compare the 90 mg group to the 27 mg group at each timepoint overall and for CKD patients and healthy volunteers separately.

Sample SAS code is as follows:

```
PROC FREQ;
  BY visit;

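### The CKD-only biomarker MMRM has no CKD stage term: possible loss of precision with all cohorts filled, and a biased 90 v 27 mg contrast if stage 4 runs at 27 mg but not in full at 90 mg

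*SAP*

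**What the plan says.** SAP 7.6.1 lists three analysis sets for percent change in the response biomarkers. The one for CKD is "A 2-way MMRM pooling stage 3 and stage 4 CKD patients together". The terms are the same for every set: "The model will include dose level, visit (2, 4, 8, 12, 18, 24, 48, 72, 96 and 168 hours), and dose-by-visit interaction as factors", plus the baseline biomarker as covariate. The sample code agrees: "MODEL resp = base visit dose dose*visit / DDF=KR". Its BY variable separates only pooled, CKD and healthy subjects, so stage does not enter that way either.

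Section 7.6.2 (absolute change) carries the model over: "The method of analysis will be identical after replacing variable". The responder GEE in 7.6.3 uses the same terms: "MODEL resp(EVENT='1') = base visit dose dose*visit / LINK=LOGIT DIST=BIN". The exploratory CMH test in 7.6.4 stratifies by baseline quintile only, although Protocol 11.3 also allowed primary diagnosis as a stratum. SAP 12 repeats the tables for CKD and for healthy subjects, not for each stage.

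Elsewhere the SAP treats stage as structural. Section 7.1 sorts listings by "stratum (CKD Stage 3 patients and CKD Stage 4 patients versus healthy volunteer subjects", and 7.2 and 7.3.1 use the same stratum for disposition and demographics. SAP 3 enrols stage 3 first, 6 subjects at 27 mg and then 6 at 90 mg. After that, "the Data and Safety Monitoring Board (DSMB) will determine whether to proceed to the stage 4 CKD cohorts", which have the same sizes and the same dose order. A further DSMB review stands between the two doses.

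**The concern.** A factor that defines the cohorts is left out of the model that compares doses within them. If the two stages respond differently, that difference goes into the residual. If the stages are also unevenly spread over the doses, it goes into the dose contrast as well.

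CKD subjects receive only 27 mg and 90 mg, so 90 v 27 mg is the only dose comparison that the plan can make in CKD. Establishing an optimal dose is among the primary objectives. Allocation to dose is by sequential cohort, not by randomisation, so balance over stage depends on every cohort being opened and filled. The design does not guarantee this.

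**Working it through.** **Inputs from the documents.** Cohort sizes (SAP 3): 3 × 6 healthy + 2 × 6 stage 3 + 2 × 6 stage 4 = 42, of which 24 have CKD. This reproduces the stated total. Confidence level: 95% (7.6.1). No power, SD or effect size is given (SAP 8), so there is no further figure to reproduce.

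**Assumption.** D is the stage 4 minus stage 3 difference in mean biomarker change, in units of the within-stage SD, taken as 0.5 / 1 / 1.5. Steps 1 to 3 are for one visit without the baseline covariate. Layouts are written as stage 3 at 27 / stage 3 at 90 / stage 4 at 27 / stage 4 at 90.

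**1. All four cohorts filled (6/6/6/6).** Each dose has 6 + 6, so the stage difference cancels and bias is 0 for any D.
- With stage: SE = √(1/12 + 1/12) = 0.408. On 21 df (t = 2.080) the half-width is 0.849 SD.
- Without stage: the expected residual variance is 1 + 24 × (D²/4)/22 = 1 + 6D²/22, on 22 df (t = 2.074).
- CI width ratio, without to with stage = √(1 + 6D²/22) × 2.074/2.080.

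| D (SD) | Ratio |
|---|---|
| 0 | 0.997 |
| 0.5 | 1.031 |
| 1 | 1.125 |
| 1.5 | 1.267 |

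The stage term costs about 0.3% in width if stage does not matter. It breaks even near D = 0.14.

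**2. Stage 4 run at 27 mg, not at 90 mg (6/6/6/0).** The 27 mg mean is half stage 4 and the 90 mg mean is all stage 3.
- Without stage: bias = 0 − D/2, that is −0.25 / −0.50 / −0.75 SD. True SE = √(1/12 + 1/6) = 0.500.
- With stage: bias is 0. The contrast rests on the stage 3 subjects, 6 v 6, so SE = √(1/6 + 1/6) = 0.577. On 15 df (t = 2.131) the half-width is 1.231 SD.
- Mean squared error: 0.25 + D²/4 without stage and 0.333 with it. They are equal at D = √(4 × 0.0833) = 0.58.
- CI half-width without stage at D = 1: 0.5 × √(1 + 3/16) × 2.120 = 1.155 SD. It stays narrower than 1.231 up to about D = 1.4.

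**3. Other layouts.** If stage 4 never opens (6/6/0/0), bias is 0. If stage 4 at 90 mg stops at 3 of 6, the 90 mg group is 3/9 stage 4 and bias = D(1/3 − 1/2) = −D/6.

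**4. Baseline as covariate, 6/6/6/0.** This was simulated with an assumed baseline–change correlation of 0.3.
- Baseline equal between stages: bias stays at about −D/2. Coverage of the 95% CI is about 93 / 88 / 82%.
- Baseline 1 SD higher in stage 4: the pooled within-dose slope is about (0.3 × 16 + 3D)/(16 + 3), and half of it offsets the bias. At D = 1: −0.50 + 0.5 × 7.8/19 = −0.295. Over the three values, simulated bias is −0.08 / −0.30 / −0.50 SD and coverage about 95 / 92 / 89%.
- This relief needs the baseline difference to act in the same direction as D. With baseline 1 SD lower in stage 4, the slope is (4.8 − 3D)/19 and bias = −D/2 − 0.5 × slope = −0.34 / −0.55 / −0.76 SD.

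**5. Over visits, 6/6/6/0.** This used generalised least squares over 10 visits (compound symmetry 0.6; autoregressive 0.8). If D rises from 0 at the first visit to 2 SD at the last, a stage main effect alone leaves bias of +0.5 SD at the first visit and −0.5 SD at the last. Stage plus stage-by-visit removes it.

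**The case against.** The strongest reply is that all of this is conditional. Neither document says that biomarker change differs by stage, and the objectives name stage 3-4 as one group, which is compatible with pooling. In the layout that the plan intends, the contrast is unbiased whatever D is, and at D = 0.5 the gain from adjusting is only 3% in CI width. The bias needs one pattern: stage 4 opened, 27 mg run, and 90 mg missing or incomplete. The documents give no probability for it. In that pattern the stage term does not improve precision, and for D below 0.58 the unadjusted contrast has the smaller mean squared error. There is no formal sample size and no multiplicity control, so error rates do not describe a confirmatory test. Listings already sort by stage, and the table specifications are in a separate document.

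Most of this stands and limits the point. It does not remove it. The gating allows the pattern, the direction of the trade-off can be stated now, and choosing the model after seeing which cohorts opened would be a post hoc decision. Listings give no stage-adjusted contrast.

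A reader might infer that the planned CKD comparison is biased as it stands, or that any unopened stage 4 cohort biases it. The documents support neither. Because 27 mg comes first, only the 90 mg cohort can be missing alone, and with no stage 4 cohort at all there is no bias. A reader might also carry these figures over to the responder GEE. That does not follow: adding a covariate to a logit model changes the odds ratio being estimated, and model stability with 24 subjects has not been examined.

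**Conclusion.** The point holds in conditional form for the CKD-only MMRM in 7.6.1 and 7.6.2. Leaving out stage costs CI width when all four cohorts are filled: little below about D = 0.5, and material from about D = 1. It costs validity in one layout that the design permits, where the bias is half the stage difference, or one sixth of it if the last cohort stops at 3 of 6. Baseline adjustment may absorb part of the bias but cannot be relied on to remove it.

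The existence of the bias in that layout, given D ≠ 0, is algebra. Its size rests wholly on the assumed D, and the simulated figures also rest on the assumed correlation and baseline shift. Stage is entangled with calendar time because the cohorts are sequential, so a stage term adjusts for both and cannot separate them. The point does not concern the model that pools CKD and healthy subjects. It is a worthwhile and cheap correction, not a fatal flaw.

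**What to change.** 1. In 7.6.1 and 7.6.2, add CKD stage (3, 4) and stage-by-visit as fixed factors to the CKD-only MMRM, in both text and code. A main effect alone is not enough if the stage difference changes over time.
2. Add a descriptive table of biomarker change by dose within stage.
3. State in advance that, if stage 4 at 90 mg is not run or is part-filled, the CKD 90 v 27 mg contrast is reported from the stage-adjusted model, and that if it is not run this is in effect a stage 3 comparison of 6 v 6.
4. For 7.6.3, give responder counts by dose and stage descriptively. A stage term in the GEE is not required.

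Cost: 1 df per visit with full cohorts (about 0.3% in CI width at a single visit if stage does not matter) and the extra tables. If stage 4 at 90 mg is missing, the SE rises from 0.50 to 0.58 SD, which is the price of removing the bias. Stage is already determined at eligibility, so no new data are needed.

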### **Study Hypothesis:**

It is hypothesized that SnPP is safe and well tolerated up to the top dose of 90 mg SnPP. It is also hypothesized that SnPP will modulate biomarker levels in a dose-related fashion.

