3 STUDY OVERVIEW

This is a Phase 1b, single-center, dose-escalating study to evaluate the safety, tolerability, PK and pharmacodynamic effect of SnPP in healthy volunteers and in subjects with stage 3-4 CKD. The following biomarkers will be used as surrogate measures of cytoprotective activity: Haptoglobin, Ferritin, Bilirubin, Hemopexin, IL-10, and Heme Oxygenase-1. Additionally, the P21 biomarker will be monitored at various points of the study as well as urine biomarker response to SnPP.

Subjects who meet all inclusion criteria and none of the exclusion criteria are eligible to be enrolled into the study.

The study is designed as follows:

- A screening period with baseline evaluations for study eligibility.
- If subjects meet eligibility criteria, they will receive SnPP by slow intravenous injection over a 120-minutes on study day 1.
- Subjects will stay in the clinic for the initial 24 hours after administration of SnPP and will be discharged at the end of study day 2 if no safety issues appear.
- The study will initially be dose-escalating in 3 groups of 6 healthy volunteers each, for a total of 18 healthy volunteers, evaluating escalating single dose of SnPP starting with a dose of 9 mg SnPP, followed by 27 mg SnPP, and 90 mg SnPP. Dose-escalation from one dose level to the next will only be allowed after a careful review of the safety, tolerability and PK data from the prior dose group as determined by the Data and Safety Monitoring Board (DSMB).
- After a careful review of the safety, tolerability and PK data from all dose groups from the healthy volunteer cohorts, the Data and Safety Monitoring Board (DSMB) will determine whether to proceed to the CKD cohorts. If the determination by the DSMB allows to proceed to the CKD cohorts, subjects with stage 3 CKD will be in 2 groups of 6 each, for a total of 12 subjects, evaluating escalating single dose of SnPP starting with a dose of 27 mg SnPP followed by 90 mg SnPP. Dose-escalation from one dose level to the next will only be allowed after a careful review of the safety, tolerability and PK data from the prior dose group as determined by the Data and Safety Monitoring Board (DSMB).

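### No dose-response analysis is pre-specified for the dose-related hypothesis, and the one planned full-range contrast in all subjects (pooled 90 v 9 mg) is confounded with population

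*SAP*

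**What the plan says.** The Study Hypothesis in the protocol synopsis reads: "It is also hypothesized that SnPP will modulate biomarker levels in a dose-related fashion". Biomarker effect and choice of an optimal dose are both listed as primary objectives.

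For the biomarkers, SAP 7.6.1 fits an MMRM with dose as a class factor, visit, their interaction, and baseline as covariate. It is run three times: all subjects ("A 2-way MMRM pooling stage 3 and stage 4 CKD patients and healthy subjects together"), CKD only, and healthy only. The MODEL statement has no term for healthy, CKD 3 or CKD 4.

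On comparisons the SAP says: "The between dose comparison will be performed using contrast in the main effect and the simple contrast at each time point", and "The difference in LSM between doses and the 95% CI for the difference will also be presented". The code line "LSMEANS dose / DIFF CL" produces every pairwise dose difference, so 90 v 9 mg is planned in the pooled and healthy runs. Both coded ESTIMATE labels name 90 v 27 mg. However, the overall one has coefficients `1 0 -1`, which under the stated coding is 9 v 90 mg.

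The exploratory test in SAP 7.6.4 is narrower: "Analysis will compare the 90 mg group to the 27 mg group at each timepoint overall and for CKD patients and healthy volunteers separately".

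On dose response itself there is one sentence: "Dose response relationship will be examined graphically and may be analyzed where appropriate". SAP Amendment 1 redefines baseline and leaves this unchanged.

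**The concern.** The hypothesis is about a relationship across doses, and the plan does not say what quantity will estimate it. An optional analysis with no named model or trigger, in an open-label trial, can be chosen after the data are seen.

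The categorical output does not fill the gap cleanly. The allocation is unbalanced by population: "The study will initially be dose-escalating in 3 groups of 6 healthy volunteers each, for a total of 18 healthy volunteers", one group at each of 9, 27 and 90 mg, while each CKD stage has six subjects at 27 mg and six at 90 mg. The pooled 9 mg group is therefore entirely healthy, and the pooled 27 and 90 mg groups are two-thirds CKD. A difference in biomarker response between CKD and healthy subjects would appear in the pooled 90 v 9 mg difference as if it were a dose effect.

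**Working it through.** The documents give no power, SD or effect size, so there is no planned figure to reproduce. The head count agrees: 18 + 12 + 12 = 42, or 6, 18 and 18 subjects at 9, 27 and 90 mg.

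**Assumptions not in the documents:** two-sided 5% level; equal between-subject SD (set to 1) across doses and populations; no dropout; one value per subject (a visit average or a single time). Power is from the noncentral t.

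**1. Confounding of pooled 90 v 9 mg.** Assume no dose effect and a CKD-healthy shift of 1 SD that remains after the baseline covariate.
- Bias = (12/18) × 1 − 0 = 0.667 SD.
- SE = √(1/18 + 1/6) = 0.471, so the noncentrality is 0.667/0.471 = 1.414. With 39 df the rejection rate is 28%.
- The unmodelled shift also inflates the residual variance by 2 × (12 × 6/18)/39 = 0.205. The noncentrality falls to 1.414/√1.205 = 1.288, and the rate to 24%. A simulation of this case gave 22%, still more than four times the nominal 5%.
- Calculated the same two ways, a shift of 0.5 SD gives 10 to 11%, and 1.5 SD gives 40 to 54%.
- Pooled 90 v 27 mg is not biased, because both doses have the same population mix.
- An unadjusted pooled slope would also be biased, rejecting about 16% at a 1 SD shift. The slope needs the population term too.

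**2. Precision of the population-adjusted slope.** With x = ln(dose) = 2.197, 3.296 and 4.500, the within-population sums of squares are:
- healthy: 6 × (1.134² + 0.035² + 1.169²) = 15.92
- each CKD stage: 12 × 0.602² = 4.35
- total: 15.92 + 2 × 4.35 = 24.61 (using unrounded terms), so SE = 1/√24.61 = 0.202 SD per ln(dose)

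**3. Power under a log-linear response of 0.5 SD per ln(dose).** The 90 − 9 difference is 0.5 × ln 10 = 1.151 SD, and the 90 − 27 difference is 0.5 × 1.204 = 0.602 SD.
- Adjusted slope: 0.5/0.202 = 2.48, 38 df, power 68%.
- Adjusted 90 v 9 mg: SE = √(0.25 × 2/18 + 1/12 + 1/6) = 0.527; 1.151/0.527 = 2.18; power 57%.
- 90 v 27 mg: SE = √(2/18) = 0.333; 0.602/0.333 = 1.81; power 42%.
- Pooled 90 v 9 mg as planned, unadjusted: 1.151/0.471 = 2.44; power 66%, but subject to the bias in step 1.

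The effect size is assumed, so the range is:

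| Slope, SD per ln(dose) | Adjusted slope | Adjusted 90 v 9 | 90 v 27 |
|---|---|---|---|
| 0.25 | 23% | 19% | 14% |
| 0.50 | 68% | 57% | 42% |
| 0.75 | 95% | 89% | 75% |

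**4. Within one population.** In healthy volunteers the slope and 90 v 9 mg have the same noncentrality (1.995 and 1.994; power 47% and 46%). In CKD there are only two doses, so the slope and 90 v 27 mg are the same test.

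**5. Other shapes, same 1.151 SD between 9 and 90 mg, population-adjusted.**
- Plateau from 27 mg: fitted slope 6 × 1.151 × (1.169 − 0.035)/24.61 = 0.318; 0.318/0.202 = 1.58; power 34%, against 57% for 90 v 9 mg (and for 27 v 9 mg).
- Effect at 90 mg only: fitted slope 6 × 1.151 × (1.169 + 2 × 0.602)/24.61 = 0.666; 0.666/0.202 = 3.30; power 90%, against 92% for 90 v 27 mg (1.151/0.333 = 3.45).

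**The case against.** The strongest reply is that the plan already looks at dose in several ways. It has visit-averaged main-effect contrasts, all pairwise LSM differences with 95% intervals, plots by dose, and separate CKD and healthy models that are free of the healthy-CKD mixing. In an open-label Phase 1b trial with no formal sample size and no decision rule tied to a biomarker p-value, keeping dose categorical is defensible. A single slope could hide a plateau, which matters for an optimal-dose objective.

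Much of this stands. It is why the slope should sit beside the categorical analysis and not replace it. A reader might infer that the trial has no answer at all to its hypothesis; the overall contrasts and LSM differences show that this goes too far. A reader might also infer that a log-dose slope clearly beats every planned pairwise contrast. It does not: pooled 90 v 9 mg as planned has 66% nominal power against 68%, and other shapes reverse the ranking.

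What does not stand is reliance on that 66%, because the contrast mixes dose with population. It is fair to say that the missing population term is a separate defect from the missing dose-response model. Adding the term to both analyses still leaves 57% against 68% under log-linearity.

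The power model in protocol 11.5 does not fill the gap. It concerns Cmax and AUC for escalation, not biomarkers.

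**Conclusion.** The concern holds in a limited form. The hypothesis is dose-related, the SAP pre-specifies no dose-response estimate for the biomarkers, and its one full-range contrast in all subjects is confounded with population. The size of that confounding depends on the CKD-healthy shift, which the documents do not give.

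The main benefit of the slope is a defined, population-adjusted answer, one per biomarker, in a plan that otherwise offers many differences over ten times. The power gain is secondary: 11 points over adjusted 90 v 9 mg and 26 over 90 v 27 mg at 0.5 SD per ln(dose), conditional on approximate log-linearity and the assumptions listed with the calculations. This is a gap worth closing; it does not invalidate the planned analyses.

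**What to change.** In SAP 7.6.1, replace the optional sentence with a pre-specified MMRM for each response biomarker: ln(dose) as a continuous term, population (healthy, CKD 3, CKD 4), visit, ln(dose)-by-visit, and baseline. Report the visit-averaged slope with its 95% CI as the dose-response result, plus a slope-by-population estimate.

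Keep the categorical pairwise differences beside it, with population added to the pooled model, so that a plateau or a top-dose-only effect remains visible. Correct the coefficients or the label of the overall ESTIMATE at the same time.

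The cost is SAP wording, one added factor in the pooled model and one extra model per biomarker. The drawback is reliance on approximate log-linearity, which the planned plots and the categorical differences can check. If the biomarker data have already been examined by dose, label the slope analysis post hoc.

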4 EFFICACY, PHARMOCOKINETIC, AND SAFETY VARIABLES

Efficacy Variables

- Percent change from baseline in biomarkers at each postbaseline time point
- Change from baseline in biomarkers at each postbaseline time point

The biomarkers include the following pharmacodynamic variables

- Haptoglobin (Hp)
- Ferritin
- Bilirubin
- Hemopexin
- IL-10
- Heme Oxygenase 1 (HO-1)
- P21

The urine biomarkers include the following pharmacodynamic variables

- Hemopexin
- Ferritin
- P21
- Heme-Oxygenase 1 (HO-1)

Pharmacokinetic (PK) Variables

- Maximum serum concentration (C_{max})
- Time to maximum serum concentration (T_{max})
- Area under the concentration-time curve from 0 to last time point (AUC_{0-t})
- Area under the concentration-time curve from 0 to infinity (AUC_{0-inf})
- Terminal elimination rate constant (λ_z)
- Terminal elimination half life (T_{1/2})
- Clearance (CL)
- Volume of distribution (V_z)

- Renal excretion and renal clearance (CL) of tin

Safety Variables

- Treatment-emergent adverse events
- Infusion-related reactions
- Clinical laboratory tests
- ECG
- Vital signs
- Physical exams
- Concomitant medications

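### SAP 7.6.1 sample code: the contrast labelled 90 mg v 27 mg overall computes 9 mg minus 90 mg, three-dose coefficients do not map safely to the two-dose CKD fit, and text and code name different covariance structures

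*SAP*

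**What the plan says.** SAP 7.6.1 plans a mixed model for repeated measures of percent change, with dose, visit, dose-by-visit and baseline. It is fitted to all subjects pooled, to CKD subjects and to healthy volunteers. The prose asks for dose comparisons overall and at each of 10 timepoints, with LS-mean differences and 95% confidence intervals.

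The code is introduced with the words "A sample SAS code is provided as follows". It runs by population, and dose "is coded as 1 = 9 mg SnPP, 2 = 27 mg SnPP, and 3 = 90 mg SnPP". The lines that matter are:

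- overall contrast: "ESTIMATE '90 mg v 27 mg overall' dose 1 0 -1"
- contrast at 168 h for the same pair: "ESTIMATE '90 mg v 27 mg @ 168 hours ' dose 0 -1 1", followed by 30 interaction coefficients
- LS means: "LSMEANS dose / DIFF CL"

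Section 7.6.2 extends this to absolute change: "The method of analysis will be identical after replacing variable". Section 3 gives healthy volunteers 9, 27 and 90 mg, and gives stage 3 and stage 4 CKD subjects only 27 and 90 mg.

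On covariance, the 7.6.1 prose names Toeplitz and the code has `TYPE=UN`. The note after the code lists Toeplitz, AR(1) and compound symmetry, to be tried in order depending on convergence, with the first that converges taken as final. Amendment 1 changes the baseline definition and the tables that depend on it, and leaves the rest of the SAP as it was.

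**The concern.** The label and the coefficients of the overall contrast name different dose pairs, and the same block uses other coefficients for the same pair at 168 h. In a three-dose fit nothing in the output would flag this, because the row is estimable and prints normally. The protocol synopsis states "It is also hypothesized that SnPP will modulate biomarker levels in a dose-related fashion". If that means LS means ordered by dose, the mislabelled row has the opposite sign to 90 minus 27 mg and is at least as large.

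The CKD fit is a second problem. Three dose coefficients are supplied where two doses exist, so repairing the label or the three-dose coefficients alone does not secure the CKD contrast.

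The covariance conflict is a separate matter and reaches further, because standard errors, Kenward-Roger degrees of freedom and intervals in the LSMEANS output depend on the structure as well.

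**Working it through.** **1. The overall contrast.** Inputs are the dose coding and the two ESTIMATE lines in SAP 7.6.1. Write m9, m27 and m90 for the overall LS means. The illustrative values are assumptions.

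| Coefficients | Meaning | Means 10/30/60 | Means 60/30/10 |
|---|---|---|---|
| 1 0 -1 (coded, labelled 90 v 27) | m9 - m90 | 10 - 60 = -50 | 60 - 10 = +50 |
| 0 -1 1 (as in the 168 h line) | m90 - m27 | 60 - 30 = +30 | 10 - 30 = -20 |

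In general, m9 - m90 = -[(m90 - m27) + (m27 - m9)]. If the means are ordered by dose, in either direction, the two bracketed terms share a sign. The coded row is then opposite in sign to m90 - m27 and at least as large.

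Rows affected if the code is run as written for the 7 blood biomarkers in SAP Section 4, on both scales, in the healthy and pooled fits: 7 x 2 x 2 = 28. Section 4 also says "The urine biomarkers include the following pharmacodynamic variables" and lists 4. If these are analysed the same way (an assumption), the count is 11 x 2 x 2 = 44.

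**2. The CKD fit.** Every cell mean in this model carries an intercept coefficient of 1 and dose coefficients that sum to 1. An estimable contrast with no intercept term therefore needs dose coefficients that sum to 0. Two behaviours are assumed, and SAS was not run: surplus coefficients are ignored, and main-effect coefficients are spread evenly over the dose-by-visit cells.

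- Class levels set within each population, so two doses:
  - The overall line becomes (1, 0), sum 1: non-estimable.
  - The three-dose repair 0 -1 1 becomes (0, -1), sum -1: non-estimable.
  - The 168 h line has the same dose part, (0, -1): non-estimable.
  - (-1, 1) sums to 0 and is estimable, as is its 168 h version with -1 and +1 in the 10th and 20th of 20 interaction cells.
- An empty 9 mg level kept: the overall line puts weight on a dose without data and is non-estimable. The 168 h line, and 0 -1 1 for the overall contrast, are estimable.

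Missing CKD rows for the 7 blood biomarkers on two scales: 7 x 2 = 14 if only the overall line fails, and 7 x 2 x 2 = 28 if the 168 h line fails too. With the urine biomarkers: 11 x 2 = 22, and 11 x 2 x 2 = 44.

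**3. Covariance parameters for 10 visits.** Unstructured: 10 x 11 / 2 = 55. Toeplitz: 10. AR(1) and compound symmetry: 2 each. Planned subjects are 18 healthy, 24 CKD and 42 pooled.

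The note can be read in two ways:

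- As the whole sequence, it starts at Toeplitz. It then agrees with the prose, and the code is out of line.
- As fallbacks, it follows the unstructured matrix in the code immediately above it. It then agrees with the code, and the prose is out of line.

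Under the first-to-converge rule, the two readings can end at different structures.

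**The case against.** The strongest reply is that the intended comparison is clear and the correct result is already requested. The block is a sample and codes one timepoint of ten. The overall ESTIMATE line does not ask for confidence limits, whereas the LSMEANS line does, so the row that meets the prose is the LSMEANS difference. Section 7.6.4 also names 90 v 27 mg as its comparison. Table specifications sit in a separate document (SAP Section 11). All of this stands, and it keeps the weight low. It does not make the coded line correct.

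Four stronger readings are tempting, and the documents do not support them:

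- A reader might infer that the trial will report a reversed 90 v 27 mg result. Nothing shows that the ESTIMATE row feeds a table. The clash with LSMEANS may also not be one of sign: if that difference is printed as 27 minus 90, the example gives -30 beside -50, and only the size differs.
- A reader might infer that 7.6.2 necessarily contains the error. It carries over the method, whose prose is right. The error follows only if the code is reused.
- A reader might infer wrong numbers for CKD. On the stated assumptions the failure is a missing estimate, which shows itself, and LSMEANS still gives the CKD difference.
- A reader might infer that prose and note agree on Toeplitz, so that the code alone is wrong. The note also reads naturally as fallbacks after the code, and 7.6.3 assumes an unstructured matrix in a model it calls similar. On the other side, the 7.6.1 prose never mentions an unstructured matrix. The point is an ambiguity.

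**Conclusion.** The overall contrast is wrong as written: under the SAP's own coding it is 9 mg minus 90 mg under a 90 v 27 mg label. This needs no assumption. If the code is run unchanged and reused for absolute change, it gives 28 mislabelled rows for the blood biomarkers, or 44 with urine.

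The CKD problem is conditional on how the software handles surplus coefficients and class levels, which the documents do not state. It amounts to 14 to 28 missing rows, or 22 to 44 with urine.

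The covariance conflict is real, at 10 parameters in the prose against 55 in the code. The starting structure can determine the reported standard errors and intervals, but no effect on any particular interval has been calculated.

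Severity is minor, because the correct overall 27 v 90 mg difference and its interval are already requested in every fit.

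**What to change.** - In the healthy and pooled fits, code the overall contrast as `dose 0 -1 1`.
- For CKD, use a separate step with `dose -1 1` and 20 matching interaction coefficients. Alternatively, take the dose differences at each visit from `LSMEANS dose*visit / DIFF CL` and keep only same-visit pairs: 3 x 10 = 30 of 30 x 29 / 2 = 435 pairs in the three-dose fits, and 10 of 20 x 19 / 2 = 190 in CKD.
- State one starting covariance structure and one fallback order, identically in prose, code and note. The choice is the sponsor's.

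The cost is a few lines of SAP text and sample code, plus a filter on the output if the LSMEANS route is taken. Data, design and sample size are unaffected.
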